#### **8.5.1.2.2 PALATABILITY AND ACCEPTABILITY OF LENVATINIB SUSPENSION FORMULATION**

The palatability and acceptability of lenvatinib suspension formulation will be assessed using the Palatability Questionnaire (see [Appendix 5](#)). All subjects who receive suspension formulation with the exception of subjects using a nasogastric or gastrostomy tube, must complete the questionnaire according to the Schedule of Assessments. If the subject is unable to complete the questionnaire, this must be done by a parent or legal guardian. Measurement of palatability will be assessed using the Hedonic scale ([Guinard, 2001](#)) which is a Visual Analog Scale (VAS).

#### **8.5.1.3 Pharmacokinetic, Pharmacodynamic, and Other Biomarker Assessments**

##### **8.5.1.3.1 PHARMACOKINETIC ASSESSMENTS**

Blood samples (2 mL each) will be collected from all subjects from Arm A only at the time points shown in [Table 3](#). Pharmacokinetic blood samples will also be drawn pretreatment on the day of tumor assessment as described in the [Table 3](#). Actual time and date of PK blood collection as well as time of drug administration will be recorded on the appropriate page of the CRF. Exposure parameters such as area under the concentration  $\times$  time curve (AUC) will be derived from posterior estimates of the PK parameters from the final population PK

model. For the time points shown in Table 3, subjects or their parents will be instructed not to take the dose of lenvatinib prior to arriving at the study site. Lenvatinib capsule administration will be recorded in the eCRF. The Cycle 1 Day 1 and Day 15 doses of lenvatinib will be administered at the study site at approximately the same time of day in order to accommodate PK sample collection timing. Instructions for the collection, handling, and shipping procedures of PK samples will be provided in a separate Laboratory Manual.

**Table 3 Lenvatinib Pharmacokinetic Sampling Time Points**

Time Point a	Time (h)
Cycle 1 Day 1	Postdose: 0.5-4 and 6-10
Cycle 1 Day 15	Predose Postdose: 0.5-4 and 6-10
Cycle 2 Day 1	Predose

Note: All predose samples are to be drawn approximately 24 hours following the dose administered on the previous day.

h = hour(s).

a. If dose interruption is necessary in these time points, please contact the sponsor.

Only samples from all subjects randomized to Arm A will be collected. Lenvatinib will be quantified using a validated liquid chromatography/mass spectrometry/mass spectrometry (LC/MS/MS) method.

#### 8.5.1.3.2 PHARMACODYNAMIC AND OTHER BIOMARKER ASSESSMENTS

Pharmacodynamic serum and archived fixed tumor tissue samples for biomarker analysis will be collected from study subjects randomized to Arm A (ie, lenvatinib + ifosfamide + etoposide), as specified in the Schedule of Procedures/Assessments. Pharmacodynamic serum and tumor biomarkers identified in other lenvatinib clinical studies will be assessed in samples collected from subjects enrolled in this study. Pharmacodynamic biomarker analysis will be performed as described in an analysis plan provided separately.

Blood biomarker samples may be used for exploratory analysis for evaluation of response-related and/or safety-related outcomes as well as for potential use in diagnostic development (see [Appendix 11](#)).

#### 8.5.1.4 Safety Assessments

Safety assessments will consist of monitoring and recording all AEs, including all grades per National Cancer Institute (NCI) CTCAE v5.0 (for both increasing and decreasing severity), and serious adverse events (SAEs); regular laboratory evaluation of hematology, blood chemistry, and urine values; periodic measurement of vital signs and 12-lead ECGs; and echocardiograms, Lansky play score or Karnofsky performance status score, physical examinations, and height assessments as detailed in the Schedule of Assessments ([Table 5](#) and [Table 6](#)).

Clinical and laboratory toxicities/symptomatology will be graded according to CTCAE v5.0 ([Cancer Therapy Evaluation Program, 2017](#)).

#### 8.5.1.4.1 ADVERSE EVENTS

An AE is any untoward medical occurrence in a patient or clinical investigation subject administered an investigational product. An AE does not necessarily have a causal relationship with the medicinal product. For this study, the study drug is lenvatinib.

The criteria for identifying AEs in this study are:

- Any unfavorable and unintended sign (including an abnormal laboratory finding), symptom, or disease temporally associated with the use of an investigational product, whether or not considered related to the investigational product (Note: Every sign or symptom should not be listed as a separate AE if the applicable disease [diagnosis] is being reported as an AE)
- Any new disease or exacerbation of an existing disease. However, worsening of the primary disease should be captured under efficacy assessments as PD.
- Any deterioration in nonprotocol-required measurements of a laboratory value or other clinical test (eg, ECG or x-ray) that results in symptoms, a change in treatment, or discontinuation of study drug
- Recurrence of an intermittent medical condition (eg, headache) not present pretreatment (Baseline)
- An abnormal laboratory test result should be considered an AE if the identified laboratory abnormality leads to any type of intervention, withdrawal of study drug, or withholding of study drug, whether prescribed in the protocol or not

All AEs, regardless of relationship to study drug or procedure, should be recorded beginning from the time the subject signs the study ICF through the last visit and for 30 days after the subject's last dose. Refer to [Section 8.5.4.1](#) for the time period after the end of treatment for SAE collection.

Abnormal laboratory values should not be listed as separate AEs if they are considered to be part of the clinical syndrome that is being reported as an AE. It is the responsibility of the investigator to review all laboratory findings in all subjects and determine if they constitute an AE. Medical and scientific judgment should be exercised in deciding whether an isolated laboratory abnormality should be classified as an AE. Any laboratory abnormality considered to constitute an AE should be reported on the Adverse Event CRF.

Abnormal ECG (QTcF) results, if not otherwise considered part of a clinical symptom that is being reported as an AE, should be considered an AE if the QTcF interval is more than 450 ms and there is an increase of more than 60 ms from baseline. Any ECG abnormality that the investigator considers as an AE should be reported as such.

All AEs must be followed for 30 days after the subject's last study drug dose, or until resolution, whichever comes first. Subjects with onset of an AE or deterioration of a preexisting AE during the AE collection period will be followed until resolution to baseline, start of a new anticancer treatment, or death. All SAEs must be followed to resolution or, if resolution is unlikely, to stabilization.

**Every effort must be made by the investigator to categorize each AE according to its severity and its relationship to the study treatment.**

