**Control Arm (Arm B): Ifosfamide + Etoposide**

Ifosfamide 3000 mg/m^2/day, IV, daily for 3 consecutive days (Day 1 to 3), every 21 days, for a maximum of 5 cycles.

Etoposide 100 mg/m^2/day, IV, daily for 3 consecutive days (Day 1 to 3), every 21 days, for a maximum of 5 cycles.

Before dose administration on Day 1 of each cycle and prior to a change in dose due to dose reduction, the amount of lenvatinib needed for each subject must be calculated as follows:

$$\text{Scheduled dose (mg/m}^2\text{)} \times \text{body surface area (BSA) (m}^2\text{)} = \text{lenvatinib dose (mg)}$$

Body surface area (BSA) will be calculated using the method that is accepted and customarily used by the clinical site. BSA must be calculated on Day 1 of each cycle based on the subject's current height and body weight. BSA will be used to determine the amount of lenvatinib for each subject. BSA should not be corrected for amputation. The dose should be rounded to the nearest whole number. After adjustment for BSA, the daily dose of lenvatinib should not exceed 24 mg daily.

Subjects will receive study treatment as continuous 21-day cycles in both treatment arms. Treatment cycles will be counted continuously regardless of dose interruptions. If chemotherapy administration is precluded on Day 1 of a treatment cycle, the subject may resume treatment once recovered at the discretion of investigator. Subsequent chemotherapy will be administered every 21 ( $\pm 1$ ) days starting from the timepoint it was resumed.

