#### 8.4.2.3 Labeling for Study Drug

Lenvatinib and the combination chemotherapy drugs, ifosfamide and etoposide, where supplied by the sponsor will be labeled in accordance with text that is in full regulatory compliance with each participating country and is translated into the required language(s) for each of those countries.

The following information will be provided (but not limited to):

- For clinical trial use only
- Name and address of the sponsor
- Chemical name / drug identifier
- Lot number/Batch number
- Storage conditions, expiration date if necessary

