## **Assessing Relationship to Study Treatment**

Items to be considered when assessing the relationship of an AE to the study treatment are:

- Temporal relationship of the onset of the event to the initiation of the study treatment
- The course of the event, especially the effect of discontinuation of study treatment or reintroduction of study treatment, as applicable
- Whether the event is known to be associated with the study treatment or with other similar treatments
- The presence of risk factors in the study subject known to increase the occurrence of the event
- The presence of nonstudy, treatment-related factors that are known to be associated with the occurrence of the event

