### *Classification of Causality*

The relationship of each AE to the study drug will be recorded on the CRF in response to the following question:

Is there a reasonable possibility that the study drug caused the AE?

Yes (related)      A causal relationship between the study drug and the AE is a reasonable possibility.

No (not related)    A causal relationship between the study drug and the AE is not a reasonable possibility.

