### 8.5.4 Reporting of Serious Adverse Events, Pregnancy, and Events Associated with Special Situations

#### 8.5.4.1 Reporting of Serious Adverse Events

**All SERIOUS ADVERSE EVENTS, regardless of their relationship to study treatment, must be reported on a completed SAE form by email or fax as soon as possible but no later than 24 hours from the date the investigator becomes aware of the event.**

Serious adverse events, regardless of causality assessment, must be collected for 30 days after the subject's last dose. All SAEs must be followed to resolution or, if resolution is unlikely, to stabilization. Any SAE judged by the investigator to be related to the study treatment or any protocol-required procedure should be reported to the sponsor regardless of the length of time that has passed since study completion.

The detailed contact information for reporting of SAEs is provided in the Investigator Study File.

**For urgent safety issues**, please ensure all appropriate medical care is administered to the subject and contact the appropriate study team member listed in the Investigator Study File.

It is very important that the SAE report form be filled out as completely as possible at the time of the initial report. This includes the investigator's assessment of causality.

Any relevant follow-up information received on SAEs should be forwarded within 24 hours of its receipt. If the relevant follow-up information changes the investigator's assessment of causality, this should also be noted on the follow-up SAE form.

Preliminary SAE reports should be followed as soon as possible by detailed descriptions including copies of hospital case reports, autopsy reports, and other documents requested by the sponsor.

The investigator must notify his/her IRB/IEC of the occurrence of the SAE in writing, if required by their institution. A copy of this communication must be forwarded to the sponsor and/or the designated CRO monitor to be filed in the sponsor's Trial Master File.

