#### 8.7.1.8.2 ADVERSE EVENTS

The AE verbatim descriptions (investigator terms from the CRF) will be classified into standardized medical terminology using the Medical Dictionary for Regulatory Activities (MedDRA). Adverse events will be coded to the MedDRA (Version 20.1 or higher) lower level term (LLT) closest to the verbatim term. The linked MedDRA preferred term (PT) and primary system organ class (SOC) are also captured in the database.

A TEAE is defined as an AE that emerges during treatment (and within 30 days of the last study treatment), having been absent at pretreatment (Baseline) or

- Re-emerges during treatment, having been present at pretreatment (Baseline) but stopped before treatment,  
or
- Worsens in severity during treatment relative to the pretreatment state, when the AE is continuous.

Only those AEs that are treatment-emergent will be included in summary tables. All AEs, treatment-emergent or otherwise, will be presented in subject data listings.

The TEAEs will be summarized by treatment group. The incidence of TEAEs will be reported as the number (percentage) of subjects with TEAEs by SOC and PT. A subject will be counted only once within an SOC and PT, even if the subject experienced more than 1 TEAE within a specific SOC and PT. The number (percentage) of subjects with TEAEs will also be summarized by highest CTCAE grade.

The number (percentage) of subjects with TEAEs will also be summarized by relationship to study drug (Yes [related] and No [not related]).

The number (percentage) of subjects with treatment-related TEAEs will be summarized by SOC and PT. Treatment-related TEAEs include those events considered by the investigator to be related to study treatment. The number (percentage) of subjects with treatment-related TEAEs will also be summarized by highest CTCAE grade.

Adverse events will be summarized using the Safety Analysis Set. The number of AEs and number and incidence (%) of subjects with AEs will be summarized by treatment group and

overall. To obtain the incidence (%), the number of subjects with at least 1 event and the percentage of subjects with AEs by SOC and by PT will be calculated. Incidence (%) by causal relationship with study drug and by severity (CTCAE v5.0) will also be calculated. For clinically significant events, time of onset, and recovery will be reported.

Adverse events will be summarized for descriptive purposes by age (2 to <6, 6 to <18, and ≥18), and sex.

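### The adverse event section ties causality to lenvatinib in one place and to the whole regimen in another, so the related-TEAE summaries have no single meaning, least of all in Arm B

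*Protocol*

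**What the plan says.** Section 8.5.1.4.1 opens with a definition: "For this study, the study drug is lenvatinib". Later in the same section a bold instruction reads "Every effort must be made by the investigator to categorize each AE according to its severity and its relationship to the study treatment", and the list of factors to weigh begins "Items to be considered when assessing the relationship of an AE to the study treatment are". The item to be recorded on the CRF, under Classification of Causality, then returns to the narrower term: "Is there a reasonable possibility that the study drug caused the AE". It is a single yes/no question. No per-drug item and no rule for Arm B is given.

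Section 8.4.1 makes clear that study treatment is not lenvatinib alone: "Subjects will receive study treatment as continuous 21-day cycles in both treatment arms". The study treatment row of Table 5 lists all three agents for Arm A, and ifosfamide with etoposide for Arm B.

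Section 8.7.1.8.2 plans one set of TEAEs "summarized by relationship to study drug (Yes [related] and No [not related" and also an incidence by causal relationship with study drug. It separately plans treatment-related TEAEs by system organ class, preferred term and highest grade, and defines these as events the investigator considers related to study treatment. The protocol text appears twice in the file, with the same wording on these points both times.

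**The concern.** One recorded answer has to serve two differently worded sets of summaries, and the protocol's definition and its instructions to investigators point to different answers. An investigator who follows the printed definition is asked about lenvatinib. One who follows the bold instruction and the list of factors is asked about the regimen.

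Comparing safety and tolerability between the arms is a secondary objective (Section 7.2), and the study is planned for approximately 70 sites (Section 5). If sites differ in how they take the question, a related-TEAE column mixes two quantities and cannot be compared with the other arm's. This is not a detail that can wait for the SAP. An SAP can choose a label for the table, but it cannot recover which question an investigator had in mind when the answer was recorded.

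**Working it through.** No arithmetic applies; the check is a comparison of text.

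**Step 1. What the two terms cover.** In Section 8.5.1.4.1, study drug is lenvatinib. In Section 8.4.1 and Table 5, study treatment is the assigned regimen. The terms differ in content in both arms.

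**Step 2. What the single answer means under each reading.**

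| | Study drug = lenvatinib | Study treatment = assigned regimen |
|---|---|---|
| Arm A | Yes only if lenvatinib may have caused the event | Yes if lenvatinib, ifosfamide or etoposide may have |
| Arm B | No for every event, since no lenvatinib is given | Yes if ifosfamide or etoposide may have |

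Take a neutropenia that the investigator attributes to chemotherapy. In Arm A it is not related on the first reading and related on the second. In Arm B it cannot be related on the first and is related on the second. Both columns of the table change with the reading, and Arm B's changes most.

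**Step 3. Whether the lenvatinib-only definition can be the intended one.** It does not fit the rest of the protocol.

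- Section 8.4.2.3, on labeling for study drug, covers all three agents: "Lenvatinib and the combination chemotherapy drugs, ifosfamide and etoposide, where supplied by the sponsor will be labeled". Exclusion criterion 6 (Section 8.3.2) names all three as study drugs.
- The Safety Analysis Set (Section 8.7.1.2) requires at least one dose of any study drug. If that meant lenvatinib, Arm B would drop out of the safety analysis, although Section 8.7.1.8 presents safety by treatment group.
- Study Day 1 for safety (Section 8.7.1.8) is the date of first study drug dose. Arm B would have none.

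The first item rests on agents named in the text. The other two are inferences, but the planned by-arm safety analysis forces them.

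**Step 4. Where the conflict reaches the output.** It reaches only the summaries in Section 8.7.1.8.2 that use relatedness. The TEAE summaries by system organ class, preferred term and highest grade, and those of SAEs, deaths and discontinuations, do not need the causality answer.

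**The case against.** The best counter-argument is that the context already favours the regimen reading. The bold instruction and the list of factors both say study treatment, and Section 8.7.1.8.2 defines treatment-related TEAEs on that basis. An investigator reading the whole section might well answer for the regimen, and nothing in the documents shows that any site would do otherwise. This stands in part. It means the literal result for Arm B is what one reading implies, not what will necessarily be observed. It does not remove the conflict, because the question itself uses exactly the term the section has just defined as lenvatinib.

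Second, study drug legitimately means lenvatinib in some places, notably the dose-reduction and stopping rules of Section 8.4.1.1. That is correct and limits the remedy: redefining study drug for the whole protocol could be read as extending the stopping rules for hepatic failure, thromboembolism and Grade 4 abdominal events to chemotherapy.

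Third, the CRF and its completion guidelines, which Section 8.6.1 makes binding on data collection, are not shown and may ask about each drug. If so, the practical effect would largely disappear, though the protocol text would then misdescribe what is collected.

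Fourth, the affected tables are descriptive, and attribution in an open-label trial is soft in any case. That is true, and it limits the weight of the point.

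**Conclusion.** The protocol is wrong as written on a narrow matter. Section 8.5.1.4.1 defines study drug as lenvatinib and asks its only stated causality question in that term, while instructing investigators to judge the regimen. Section 8.7.1.8.2 then reports the one answer under both labels. The related-TEAE summaries are ambiguous in both arms and most of all in Arm B, where the literal reading allows no related event. It should be corrected, but it threatens no primary conclusion.

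Three stronger readings are tempting and not supported.

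- *Arm B's related-TEAE rate will be zero.* That follows only if sites apply the definition and set aside the surrounding instructions.
- *The distortion can be sized from the earlier combination study in Section 6.3.1.* Its 48% rate of treatment-related Grade 3 or higher neutropenia comes from subjects who also took lenvatinib, and the documents give no share of sites adopting either reading.
- *Safety reporting as a whole is compromised.* SAEs are collected regardless of causality for 30 days after the last dose, and the later reporting rule is already on the wider basis: "Any SAE judged by the investigator to be related to the study treatment or any protocol-required procedure should be reported to the sponsor".

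The conclusion assumes that the question printed in the protocol is the one put to investigators.

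**What to change.** Three matching changes, confined to adverse event assessment:

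- In Section 8.5.1.4.1, replace the definition with: *For the assessment of AEs and their causality, study treatment means lenvatinib, ifosfamide and etoposide in Arm A, and ifosfamide and etoposide in Arm B.*
- Under Classification of Causality, ask: *Is there a reasonable possibility that any study treatment the subject received caused the AE?* Align the sentence introducing the question and the yes/no definitions.
- In Section 8.7.1.8.2, word every related-TEAE summary as relationship to study treatment in that sense.

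Leave study drug in Section 8.4.1.1 meaning lenvatinib, so that no stopping rule changes scope.

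Where the CRF allows, also record lenvatinib-relatedness separately in Arm A. This is preferable, because dose modification under Table 1 turns on lenvatinib-related toxicity and the combined question alone would not capture it.

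The cost is a few words in three places of an amendment, and the same rewording of the CRF item if it prints the present question. No visits, samples or subjects are added. The separate lenvatinib record would add a small number of CRF fields.

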## **Assessing Severity of Adverse Events**

Adverse events will be graded on a 5-point scale according to CTCAE v5.0 ([Cancer Therapy Evaluation Program, 2017](#)). Investigators will report CTCAE grades for all AEs (for both increasing and decreasing severity).

## **Assessing Relationship to Study Treatment**

Items to be considered when assessing the relationship of an AE to the study treatment are:

- Temporal relationship of the onset of the event to the initiation of the study treatment
- The course of the event, especially the effect of discontinuation of study treatment or reintroduction of study treatment, as applicable
- Whether the event is known to be associated with the study treatment or with other similar treatments
- The presence of risk factors in the study subject known to increase the occurrence of the event
- The presence of nonstudy, treatment-related factors that are known to be associated with the occurrence of the event

